4.1.1 Dose-limiting toxicity criteria (Part-1 and Part-3A)

Potential DLTs are defined as all AEs specified below occurring during the first cycle of treatment considered by the investigator to be related to study treatment, unless due to disease progression or to a cause obviously unrelated to IMP.

- Grade ≥ 4 AEs.
- Grade 3 neutropenia lasting > 7 days or febrile neutropenia.
- Grade 3 thrombocytopenia with clinically significant bleeding.
- Any Grade ≥ 3 immune-related AEs (irAE) (Part-1, 2, and 4 only).

An irAE can occur shortly after the first dose or several months after the last dose of treatment. All AEs of unknown etiology associated with drug exposure should be evaluated to determine possible immune etiology. If an irAE is suspected, efforts should be made to rule out neoplastic, infectious, metabolic, toxin or other etiologic causes prior to labeling an AE as an irAE.

- Grade 3 nonhematologic AEs, including rash, nausea/vomiting, hypertension, diarrhea, retinopathy, or blurred vision that remain uncontrolled (does not resolve to \leq Grade 2) for > 72 hours despite maximal supportive care. Electrolyte abnormalities or Grade 3 asymptomatic creatine phosphokinase (CPK) or gamma-glutamyl transferase (GGT) elevations that are corrected within 72 hours will not be considered DLTs.
- Grade 3AST, ALT, and/or total bilirubin elevations that persist > 5 days.

- Concurrent elevation of AST or ALT $>3 \times$ upper limit of normal (ULN) and total bilirubin $>2 \times$ ULN or international normalized ratio (INR) >1.5 in the absence of cholestasis and other causes (eg, viral hepatitis, other pre-existing or acute liver disease, or another drug capable of the observed injury), which may indicate severe drug-induced liver injury (possible Hy's law case).
- Grade 3 QTcF (defined as QT interval corrected using Fridericia's formula [QTcF] >450 msec or change from baseline of QTcF >50 msec) prolongation.
- Retinal vein occlusion (RVO) any grade
- Toxicity related to IMP leading to 50% or less dose intensity of SAR442720 (eg, miss ≥ 3 doses) and/or delay in initiation of Cycle 2 dosing of pembrolizumab by >15 days, in the absence of recovery to baseline or Grade ≤ 1 (except for alopecia, vitiligo, fatigue and thyroiditis) AE. Toxicity resulting in the inability to deliver at least 66.7% of the dose of adagrasib (Part-3A) as intended for the duration of the cycle.

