6.6.1 Dose modification criteria

6.6.1.1 General guidelines for adagrasib (Part-3)

The following are the general guidelines for withholding, resumption or re-challenge of treatment with adagrasib:

- following adagrasib dose reduction and control of an AE, re-challenge at a higher adagrasib dose may be permitted after discussion with the Sponsor;

- if resumption of dosing for adagrasib is delayed for ≥ 14 days due to an AE that is at least suspected to be attributable to study treatment, then resumption at a reduced dose should be considered;
- if treatment with adagrasib is withheld for ≥ 22 consecutive days, then permanent discontinuation from treatment with one or both agents should be considered; and
- if a treatment-related AE recurs despite dose reduction of adagrasib to the lowest dose anticipated, then permanent discontinuation from study treatment should be considered, unless after discussion with the Sponsor it is considered to be in the best interest of the participant to continue.

Treatment interruptions and modification guidelines are provided in Appendix 9 ([Section 10.9](#)).

Additional guidelines for adagrasib:

Hepatic Toxicities

Hepatic toxicities that are considered to be causally related to adagrasib should initially be managed with treatment interruption of one or both study drugs as outlined in [Table 27](#). Evaluations for confounding factors (eg, cholestasis, metastasis, or viral infection) should be performed as clinically indicated, and more frequent monitoring of a hepatic panel (including AST, ALT, alkaline phosphatase, and bilirubin) should be considered for those participants with transaminase increases. Following resolution of toxicity to the specified degree, dose reduction of adagrasib should be implemented.

Other Laboratory Investigation-Based Toxicities

Other laboratory investigation-based toxicities that are considered to be causally related to adagrasib should initially be managed with treatment interruption of adagrasib as outlined in [Table 27](#). Following resolution of toxicity to the specified degree, dose reduction of adagrasib should be implemented.

Cardiac Toxicities

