Cardiac toxicities that are considered to be causally related to adagrasib should initially be managed with treatment interruption of adagrasib as outlined in [Table 27](#). Cardiology consultation should be obtained for cases of QTcF prolongation or LVEF decreases falling into the categories indicated in [Table 27](#). In addition, more frequent monitoring of electrolytes that include potassium and magnesium should be considered for participants with vomiting, diarrhea, or past instances of hypokalemia or hypomagnesemia that could recur, and oral and/or intravenous supplementation should be considered for levels below the lower limit of normal. Additionally, arrhythmia should be included in the differential diagnosis of relevant AEs (eg, palpitations, syncope, pre-syncope, or unexplained dyspnea), and unscheduled ECGs should be performed for participants with such events or electrolyte abnormalities as clinically indicated. Additional assessments of LVEF should be performed as clinically indicated at the Investigator's discretion if there are signs or symptoms of cardiotoxicity.

Following resolution of toxicity to the specified degree, dose reduction of adagrasib should be implemented.

Pneumonitis

Pneumonitis has been reported in the Phase 1 study of adagrasib. An evaluation should be performed to assess the attribution of pneumonitis to adagrasib. Pneumonitis considered to be causally related to adagrasib should be initially managed with treatment interruption of adagrasib as outlined in [Table 27](#). Following resolution of toxicity to the specified degree, dose reduction of adagrasib should be implemented.

Other Toxicities

Other toxicities that are considered to be causally related to adagrasib should initially be managed with treatment interruption as outlined in [Table 27](#). Following resolution of toxicity to the specified degree, dose reduction of adagrasib should be implemented.

Hormonal Contraceptives and Thrombotic Events

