6.6.1.3 Management of ophthalmologic complications

The causal relationship between a change in vision and the study treatment should be carefully explored and an ophthalmologist should be consulted. Immediate consultation should be sought for Grade >1 visual changes. Special attention should be given to retinal (eg, central serous retinopathy [CSR]) or retinal vein abnormalities (eg, RVO). If consultation cannot be obtained within 7 days of onset, interrupt treatment (either SAR442720 and pembrolizumab or SAR442720 and adagrasib) until the consultation has occurred.

If RVO is diagnosed, permanently discontinue treatment (either SAR442720 and pembrolizumab or SAR442720 and adagrasib) immediately and treat per institutional guidelines. If uveitis is diagnosed, withhold treatment (either SAR442720 and pembrolizumab or SAR442720 and adagrasib) and consider use of topical steroids until resolution. If CSR or neurosensory retinal detachment is diagnosed, withhold treatment until symptoms resolve and retinal exam shows resolution. Restart medication(s) at one dose level lower and close monitoring following re-initiation of medication(s). If > Grade 1 symptoms recur or follow-up ophthalmology examination worsens, withhold treatment (either SAR442720 and pembrolizumab or SAR442720 and adagrasib) and either further decrease the dose or permanently discontinue treatment.

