 - Investigator believes that it is in the best interest of the participant to withdraw from the study
- Pregnancy
- Lost to follow-up
- Sponsor's decision to terminate the study

Participants who have stable disease as best response will be allowed to continue on treatment provided the investigator believes it is in the participant's best interest and none of the above criteria have been met.

During the conduct of the study, in cases where premature discontinuation of SAR442720 is required, the participant may continue pembrolizumab or adagrasib treatment, upon Investigator decision and in agreement with the Study Medical Manager. Likewise, in cases where premature discontinuation of pembrolizumab or adagrasib is required, the participant may continue SAR442720 treatment if there is presence of, or potential for, clinical benefit as assessed by the Investigator and Study Medical Manager.

Participants who discontinue study treatment should complete the safety follow up or EOT visit, within 30 days after the last treatment dose. Participants who do not withdraw consent will also undergo long term follow up until death or end of study or lost to follow-up.

Refer to SoA for data to be collected at the time of intervention discontinuation and follow-up and for any further evaluations that need to be completed.

Handling of participants after definitive intervention discontinuation

Participants will be followed-up according to the study procedures specified in this protocol up to the scheduled date of study completion, or up to recovery or stabilization of any AE to be followed-up as specified in this protocol, whichever comes last.

If possible, and after the definitive discontinuation of intervention, the participants will be assessed using the procedure normally planned for the last dosing day with the IMP including a PK sample, if appropriate.

All cases of definitive intervention discontinuation must be recorded by the Investigator in the appropriate pages of the eCRF when considered as confirmed.

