10.9 APPENDIX 9: GENERAL GUIDELINES FOR THE MANAGEMENT OF ADVERSE EVENTS

Investigators must be extremely vigilant and be ready to intervene early in the management of AEs, particularly immune-related AEs because the onset of symptoms of irAEs (eg, pneumonitis) may be subtle.

- Detailed guidance for the management of specific AEs (colitis, endocrine AE, pneumonitis, renal AE, dermatologic AE, hepatitis, ophthalmologic AE [uveitis], etc.) is provided in [Table 27](#).
- General guidance is provided in [Table 26](#) below.
- If a participant experiences several AEs which involve different recommendations, the most conservative recommendation should be followed.

The recommendations provided in [Table 26](#) and [Table 27](#) should be seen as guidelines, and the treating physician should exercise clinical judgment based on the symptoms and condition of the individual participant.

Table 26 - General guidelines

Severity	Withhold/restart /discontinue SAR442720 treatment	Withhold/restart/discontinue the combination drug (Pembrolizumab or adagrasib) treatment	Supportive care
Grade 1	No action	No action	Provide symptomatic treatment.
Grade 2	No action	May delay or omit the pembrolizumab dose until Grade ≤ 1 Adagrasib dose modification/ dose interruption per Investigators discretion unless otherwise defined in Table 27 .	Consider systemic corticosteroids (Prednisone 0.5 to 1 mg/kg/day or equivalent) in addition to appropriate symptomatic treatment.
Grade 3	Delay the treatment until toxicity improves to Grade ≤ 1 or baseline.		For any Grade 3-4 immune-related adverse event, if symptoms worsen or do not improve on adequate corticosteroids (prednisone 1 to 2 mg/kg/day or equivalent) within 48 to 72 hours), consider additional immunosuppressive agents (to be selected from agents such as: infliximab, cyclophosphamide, cyclosporine and mycophenolate mofetil). Referral of the participant to a specialized unit for assessment and treatment should be considered.
Grade 4	Permanently discontinue		

Table 27 - Dose modification guidelines for combination regimens (SAR442720 and pembrolizumab combination or SAR442720 and adagrasib combination)

AE	Action

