Skin reactions	
Grade 1 or 2 (tolerable): Administer supportive care and continue study drugs
 
Intolerable Grade 2-Grade 3: Hold both drugs until < Grade 2. If improves to < Grade 2 within 4 weeks, then reduce SAR442720 by one dose level and resume combination drugs at the same dose level.
 
Suspected Stevens-Johnson Syndrome (SJS) or toxic epidermal necrolysis (TEN): Withhold both drugs until adverse reactions recover to Grade 0-1.
 
Grade 4: Hold both drugs until < Grade 1. If improves to < Grade 1 within 4 weeks, resume, reduce SAR442720 by two dose levels and resume combination drugs at the same dose level.
 
Grade 4 or confirmed SJS or TEN: Permanently discontinue both drugs
 
If \geq Grade 3 rash recurs despite two SAR442720 dose level reductions, permanently discontinue both drugs.
 
If rash does not improve within 4 weeks, permanently discontinue both drugs.

Ocular symptoms > Grade 2	
Hold both study drugs and obtain ophthalmology consult.
 
RVO: Any grade, permanently discontinue both drugs (Part-1, 2, and 4 only). In Part-3 permanently discontinue SAR442720 but may continue adagrasib, please consult with the Medical Monitor.
 
Neurosensory retinal detachment: Hold both drugs until resolution to \leq Grade 1. If resolves within 4 weeks, then reduce SAR442720 by one dose level. If visual symptoms > Grade 2 recur despite two dose level reductions, permanently discontinue both drugs. (Part-1, 2 and 4 only). In Part-3 permanently discontinue SAR442720 but may continue adagrasib, please consult with the Medical Monitor.
 
Uveitis/iritis > Grade 2: Hold both study drugs. If resolves to \leq Grade 1 within 4 weeks, then reduce SAR442720 dose by one level and resume both study drugs. If recurs despite two dose level reductions of SAR442720, permanently discontinue both drugs. If > Grade 1 symptoms recur or follow-up ophthalmology examination results worsen, withhold treatment (either SAR442720 and pembrolizumab or SAR442720 and adagrasib) and either further decrease dose or permanently discontinue treatment.
 
Other > Grade 2 AE: Hold SAR442720. If AE doesn't improve within 2 weeks, then consider holding the combination drug. If no improvement within 4 weeks from onset, consider permanently discontinuing both drugs. In ambiguous cases, please consult with the Medical Monitor.

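### After retinal vein occlusion in Part-3, Section 6.6.1.3 stops adagrasib permanently while Table 27 lets it continue, and no text expressly says which rule governs

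*Protocol*

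**What the plan says.** Section 6.6.1.3 of the protocol (ophthalmologic complications) instructs: "If RVO is diagnosed, permanently discontinue treatment (either SAR442720 and pembrolizumab or SAR442720 and adagrasib) immediately". It names the Part-3 regimen and makes no exception for it.

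Table 27 in Appendix 9 covers the same event in its row on ocular symptoms. The row opens with "Hold both study drugs and obtain ophthalmology consult". Its RVO line then reads: "RVO: Any grade, permanently discontinue both drugs (Part-1, 2, and 4 only). In Part-3 permanently discontinue SAR442720 but may continue adagrasib", followed by a request to consult the Medical Monitor.

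Four other places bear on the question:

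- Section 4.1.1 lists "Retinal vein occlusion (RVO) any grade" among the DLT criteria for Part-1 and Part-3A.
- Section 6.6.1.1, the general guidelines for adagrasib in Part-3, says "Treatment interruptions and modification guidelines are provided in Appendix 9". Under its Other Toxicities heading it adds "Other toxicities that are considered to be causally related to adagrasib should initially be managed with treatment interruption as outlined in" Table 27.
- Section 7.1.1 says that "in cases where premature discontinuation of SAR442720 is required, the participant may continue pembrolizumab or adagrasib treatment", on the Investigator's decision and with the Study Medical Manager's agreement.
- The introduction to Appendix 9 presents Table 27 as the detailed guidance for specific adverse events, ophthalmologic ones included. It also describes Tables 26 and 27 as guidelines to be applied with clinical judgment, and it says: "If a participant experiences several AEs which involve different recommendations, the most conservative recommendation should be followed".

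**The concern.** A permanent stopping rule should give one answer for one event. Here an investigator who reads the body of the protocol must end adagrasib for good, while one who reads the appendix table may keep the participant on it after consultation. Two sites could manage identical cases differently. A site that uses the table's option departs from the wording of Section 6.6.1.3. A site that follows Section 6.6.1.3 permanently withdraws a KRAS G12C inhibitor that the sponsor may have meant to leave available.

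Neither sentence looks like a leftover from before adagrasib was added, since both mention it by name. The summary of changes for amendment 04 says that Part-3 management details went into both Section 6.6 and Appendix 9. Nothing in either sentence is redacted.

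**Working it through.** No figure is in dispute, so the check sets the texts side by side and then looks for a rule of precedence.

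**1. The two instructions for RVO in Part-3**

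| | Section 6.6.1.3 | Table 27, RVO line |
|---|---|---|
| SAR442720 | permanent stop | permanent stop |
| Adagrasib | permanent stop, at once | may continue, with Medical Monitor consultation |
| Grade | not qualified | any grade |
| Part-3 exception | none | yes |

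They agree on SAR442720 and differ on adagrasib. The opening line of the table row holds both drugs first, so in practice the difference is mainly whether adagrasib may be resumed. The row is headed for symptoms above Grade 2 while the RVO line covers any grade, so it is less clear that the hold applies to RVO of Grade 2 or below.

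**2. Is there a rule that decides between them?**

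- Section 6.6 sends dose modification to Section 6.6.1 without ranking that section against Table 27.
- Section 6.6.1.1 points Part-3 adagrasib management to Appendix 9. This leans toward the table but does not say that it overrides Section 6.6.1.3. The Other Toxicities paragraph covers only events judged causally related to adagrasib.
- Section 7.1.1 permits adagrasib alone once SAR442720 has to stop. It has no exclusion by event, so it also leans toward the table, but it does not mention RVO or set aside the specific instruction in Section 6.6.1.3.
- Appendix 9 leans both ways. Its detailed-guidance line supports the table; its statement that the tables are guidelines weakens any claim that they override the body text.
- The rule in Appendix 9 to take the most cautious course is written for a participant with several adverse events, not for one event with two instructions.
- The subsections on diarrhea, hypertension, liver function, LVEF, hemorrhage and rash each refer the reader to Table 27. Section 6.6.1.3 does not.

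There are cues, mostly toward Table 27, but no express precedence.

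**3. Which action satisfies both texts?** The table's wording on adagrasib is permissive. Stopping both drugs permanently therefore complies with both. Continuing or later resuming adagrasib complies with the table only.

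**4. How many participants fall under the rule?** Section 9.2 plans 15 to 30 DLT-evaluable participants in Part-3A and about 40 in Part-3B:

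- lower end: 15 + 40 = 55
- upper end: 30 + 40 = 70

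The Part-3A count is of DLT-evaluable participants, so any who are replaced would add to it. These are people to whom the rule applies, not expected cases.

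**5. Does anything statistical move?** RVO meets the DLT criterion by itself when it occurs in Cycle 1 and is judged related, whatever then happens to adagrasib. The DLT count is the same under either text, and the sample sizes and planned analyses do not depend on which rule is followed.

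**The case against.** The best defence is that the intended answer is fairly clear. Table 27 separates Part-3 from the other parts, whereas Section 6.6.1.3 uses one parenthesis for both regimens. Section 6.6.1.1 is specific to adagrasib in Part-3 and points to Appendix 9, Appendix 9 calls Table 27 the detailed guidance for eye events, and Section 7.1.1 already allows adagrasib alone. On this view Section 6.6.1.3 stands by itself, and the table's option is supervised because the Medical Monitor is consulted.

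Much of this stands. The weight of the surrounding text favours the table, and nobody is obliged to continue adagrasib. What does not follow is that the table prevails: Section 6.6.1.3 names both the event and the adagrasib regimen, and Appendix 9 itself presents the table as guidance.

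The event may also be very uncommon. Exclusion E 06 removes people with past or current RVO or with risk factors judged unacceptable. RVO is not among the SAR442720 risks in Table 11 or the adagrasib events described in Section 2.3.1.4. That limits how often the conflict could arise, but not the need for a single rule.

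Two stronger inferences are tempting. A reader might conclude that sites cannot comply with the protocol; they can, by stopping both drugs. A reader might also infer from RVO's DLT status that the MTD decision is at risk. The DLT criterion is silent on resuming adagrasib, and about 40 of the 55 to 70 participants are in Part-3B, where DLTs do not drive dose decisions.

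**Conclusion.** The inconsistency is real and sits in current text. For RVO in Part-3, one section ends adagrasib permanently and the other allows it to continue after consultation. The surrounding text leans toward Table 27 without saying that it governs.

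The consequence is confined to adagrasib treatment in Part-3 participants who develop RVO, out of about 55 to 70 planned. No case count is offered because the documents give no rate. The conclusion rests on reading both sentences as operative instructions, and nothing in the protocol marks either as superseded. It is a safety-relevant alignment of text, not a flaw in design or analysis.

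**What to change.** At the next amendment, state one Part-3 rule for RVO in both places. Either:

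- add the existing Table 27 exception to Section 6.6.1.3, so that in Part-3 SAR442720 stops permanently and adagrasib may go on after the Medical Monitor has been consulted; or
- remove the exception from the RVO line of Table 27, so that both drugs stop permanently in every part.

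The Part-3 rule for a symptomatic fall in LVEF already says the same thing in Section 6.6.1.7 and Table 27, and can serve as the pattern. Further conditions, such as holding adagrasib at any grade until ophthalmology review, are the sponsor's choice and go beyond this correction.

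Until then, a short note to Part-3 sites should say that SAR442720 and adagrasib are both stopped permanently when RVO is diagnosed. A temporary hold of both drugs is not enough, because both texts require SAR442720 to stop for good. The note withholds an option the sponsor may have intended, so the interim should be short.

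The same amendment should check the adjacent line on neurosensory retinal detachment. Section 6.6.1.3 allows a restart one dose level lower after resolution, while the table's Part-3 sentence stops SAR442720 permanently. It is unclear whether that sentence applies from the first event or only on recurrence after dose reductions.

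The cost is a sentence or two of protocol text and a site note. Section 10.1.1 requires IRB/IEC approval before an amended design is implemented, so the change is cheapest when bundled with other amendments. Design, sample size and analysis are untouched.
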